11.3.1 Assessments

Participants will be asked to undertake assessments at baseline and after they have finished the VR intervention. The timing of the follow-up period will be informed by activities and data in Phases 1 and 2 of this study. Baseline assessments will be conducted in the hospital setting, but the follow-up assessments will be completed by participants at home either on paper to be returned to the research site, or remotely. If participants are having difficulty, or are delayed in completing the

follow-up assessments, they may be contacted by the research team to support the completion of assessments over the telephone.

Assessments will include;

- Collection of baseline demographic data to understand the diversity of the participant
 population and to contextualise any additional support requirements the participant may
 require in engaging with the intervention or completing assessments. This will be obtained
 from hospital notes for participants.
- 2) Collection of intervention adherence data, such as number of days the VR headset was used, the average length of time the VR headset was used and what aspects of the content package participants engaged with most. This data will be collected continuously by the DR.VR software during the intervention period and downloaded at the end of the intervention period.

Clinical outcome	Construct	Description	Time to	Time	
measures based on			Complete	point	
the priorities of			•	•	
ICU survivors,					
their family					
members and					
HCPs involved in					
the rehabilitation of					
ICU survivors have					
been selected,					
detailed in table 1					
People with lived					
experience have					
been involved in					
the choice of					
outcome measures,					
based on perceived					
importance and					
burden of					
assessment. Name					
EQ-5D	Quality of Life	A well validated	5 mins	Baseline	ICU
		outcome measure for		and	patients
		assessing quality of life		Follow	and
		over 5 domains across;		Up	family
		usual activities, self-			members
		care, mobility, anxiety			
		and depression and			
		pain and discomfort.			

			T	T	
		Participants are also			
		asked to rate their			
		overall quality of life			
		using a visual analogue			
		scale (0-100).			
ICECAP-A	Quality of Life	Another well validated	5 mins	Baseline	
		quality of life		and	
		instrument 5		Follow	
		questions. Wellbeing:		Up	
		feeling settled and			
		secure; love, friendship			
		and support; being			
		independent;			
		achievement and			
		progress; enjoyment			
		and pleasure			
Brief resilience	Psychological	This consists of 6 items	5 mins	Baseline	ICU
Scale	resilience	relating to response or		only	patients
		coping to adverse life		J,	and
		events. Participants			family
		are asked to rate each			members
Richards Campbell	Sleep	This is a 6 item	5 mins	Baseline	ICU
Sleep	эгсер	questionnaire	3 1111113	and	Patients
Questionnaire		designed to address		Follow	only
Questionnane		sleep and sleep		Up	Omy
		·		Op	
		i dilality Participants			1
		quality. Participants			
		are asked to respond			
		are asked to respond to questions on a scale			
		are asked to respond to questions on a scale of 0-100. Questions			
		are asked to respond to questions on a scale of 0-100. Questions cover; sleep depth,			
		are asked to respond to questions on a scale of 0-100. Questions cover; sleep depth, latency, awakenings,			
		are asked to respond to questions on a scale of 0-100. Questions cover; sleep depth, latency, awakenings, ability to return to			
		are asked to respond to questions on a scale of 0-100. Questions cover; sleep depth, latency, awakenings, ability to return to sleep, sleep quality,			
		are asked to respond to questions on a scale of 0-100. Questions cover; sleep depth, latency, awakenings, ability to return to sleep, sleep quality, with an optional item			
		are asked to respond to questions on a scale of 0-100. Questions cover; sleep depth, latency, awakenings, ability to return to sleep, sleep quality, with an optional item concerning noise.			
DASS-10	Depression and	are asked to respond to questions on a scale of 0-100. Questions cover; sleep depth, latency, awakenings, ability to return to sleep, sleep quality, with an optional item concerning noise. This questionnaire	7 mins	Baseline	ICU
DASS-10	Depression and Anxiety	are asked to respond to questions on a scale of 0-100. Questions cover; sleep depth, latency, awakenings, ability to return to sleep, sleep quality, with an optional item concerning noise. This questionnaire consists of 10 items.	7 mins	and	patients
DASS-10	· •	are asked to respond to questions on a scale of 0-100. Questions cover; sleep depth, latency, awakenings, ability to return to sleep, sleep quality, with an optional item concerning noise. This questionnaire consists of 10 items. Respondents are	7 mins	and Follow	patients and

Qualitative interviews will be conducted either in person, on the telephone or via secure video-conferencing platforms such as Zoom or Teams and will be dictated by participant preference. Interviews will be audio recorded for transcription and analysis (see data management and analysis sections for further details).

Table 2. Schedule of enrolment and assessments¹

Procedures	Visits				
	Screening	Baseline	Intervention Delivery	Follow Up	
	day)	(Wk 0)	(Wk 1-2)	Wk 2	Wk 4-8
Informed consent	Х				
Demographics		х			
Eligibility assessment	х				
Outcome measures from table 1.		х		х	

¹ Taken from the HRA CTIMP protocol template (2016).

.

VR READY intervention		х	
Intervention adherence		х	
Qualitative interviews			
Phase 3 participants and			х
family members			
phase 3 delivery staff)		х	

12 Safety reporting

The PI is responsible for ensuring that all site staff involved in this trial are familiar with the content of this section.

All Serious Adverse Events (SAEs) that meet requirements of an SAE must be reported immediately (and within 24 hours of knowledge of the event) by the PI at the participating site to the VR READY study team unless the SAE is specified as not requiring immediate reporting (see section 13.2).

12.1 Definitions

Term	Definition			
Adverse Event (AE)	"Any untoward medical occurrence in a patient or clinical trial participant taking part in health care research, which does not necessarily have a causal relationship with the research."			
Serious Adverse Event (SAE)	 Any adverse event that - Results in death Is immediately life-threatening Requires hospitalisation or prolongation of existing hospitalisation Results in persistent or significant disability or incapacity Is an important medical condition (if they jeopardise the subject or require an intervention to prevent one of the above). 			
Serious Adverse Reactions (SARs)	Any SAE occurring in a clinical trial participant for which there is a reasonable possibility that it is related to the intervention.			

Suspected Unexpected	A SAR, the nature and severity of which is not consistent with the
Serious Adverse Reactions	Reference Safety Information (RSI) for the intervention.
(SUSARs)	

12.2 Study Specific SAE Reporting Requirements

In this patient population, recovering from critical illness, death, organ failure and readmission to intensive care are expected outcomes.

There are no anticipated adverse events that should be specially reported as SAEs for the purposes of this study.

12.3 Causality

Causal relationship will be assessed for the intervention and procedures:

Intervention: VR READY mediated by DR.VR

The PI (or another delegated medically qualified doctor from the trial team) will assess each SAE to determine the causal relationship and the Chief Investigator (CI) (or another appropriately qualified member of the Trial Management Group (TMG)) can also provide this assessment where necessary:

Relationship	Description	Reasonable possibility that the SAE may have been caused by the intervention?
Unrelated	There is no evidence of any causal relationship with the intervention	No
Unlikely	There is little evidence to suggest there is a causal relationship with the intervention (e.g. the event did not occur within a reasonable time after administration of the trial medication). There is another reasonable explanation for the event (e.g. the participant's clinical condition, other concomitant treatment).	No
Possible	There is some evidence to suggest a causal relationship with the intervention (e.g. because the event occurs within a reasonable time after administration of the trial medication). However, the influence of other factors may have contributed to the event (e.g. the participant's clinical condition, other concomitant treatments).	Yes

Probable	There is evidence to suggest a causal relationship and the influence of other factors is unlikely.	Yes
Definite	There is clear evidence to suggest a causal relationship and other possible contributing factors can be ruled out.	Yes

12.4 Expectedness

The clinical CI (or another delegated appropriately qualified individual) will assess each SAE to perform the assessment of expectedness.

SAEs which add significant information on specificity or severity of a known, already documented adverse event constitute unexpected events. For example, an event more specific or more severe than that described in the protocol is considered unexpected.

Expected adverse events from use of virtual reality headsets
Motion sickness (usually mild)
Headache (usually mild)

12.5 Reporting Procedures

12.5.1 Participating Site Responsibilities

The PI (or delegated appropriately qualified doctor from the research team) should sign and date the SAE CRF to acknowledge that he/she has performed the seriousness and causality assessments.

A completed SAE form for all events requiring immediate reporting should be submitted via email to the VR READY study team within **24 hours** of knowledge of the event. A separate form must be used to report each event, irrespective of whether or not the events had the same date of onset.

The participant will be identified only by trial number and initials. The participant's name should not be used on any correspondence. It is also required that sites respond to and clarify any queries raised on any reported SAEs and report any additional information as soon as it becomes available (or at least within 24 hours of the information becoming available) through to the resolution of the event. Additionally, the VR READY study team may request additional information relating to any SAEs and the site should provide as much information as is available to them in order to resolve these queries.

Serious Adverse Event (SAE) email address:

[contact]

Serious adverse events should be reported from time of signature of informed consent, throughout the treatment period up to, and including completion of the follow-up timepoint.

For each **SAE** the following information will be collected:

- full details in medical terms and case description
- event duration (start and end dates, if applicable)
- action taken
- outcome
- seriousness criteria
- causality (i.e. relatedness to intervention), in the opinion of the investigator.

An SAE form is not considered as complete unless the following details are provided:

- Full participant trial number
- An Adverse Event
- A completed assessment of the seriousness, and causality as performed by the PI (or another appropriately medically qualified doctor registered on the delegation log).

If any of these details are missing, the site will be contacted and the information must be provided by the site to the VR READY study team within 24 hours.

All other AEs should be reported on the relevant CRF in the study database following the CRF procedure described in Section 16.

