11.3 Phase 3 - Feasibility Study

Following the development of the VR intervention, its use will be piloted in a small, one arm feasibility study. Up to 25 participants will be recruited to receive the intervention for 2 weeks in the in-patient setting. If participants are discharged prior to completion of the 2-week intervention delivery, they will be able to take the headset home with them.

Following the provision of consent, participants will complete the baseline assessments. We anticipate that for the majority of participants, they will be unable to complete self-report items independently. Therefore, a member of the research team will aid completion by reading out questions and confirming the participants response, which will be entered directly into REDCap using a tablet or laptop.

Where participants are required to complete follow-up assessments at home, they will be asked for their preferred method for completion (either on paper, electronically or research team assisted via the telephone) and guidance for how to complete the assessments will be provided.

The participant will be provided with a VR headset and instructed on how to use the equipment and how to engage with the intervention. A written instruction manual will also be provided. For at least the first two days of the intervention, the participant will be assisted by a member of the research team to guide use of the VR apparatus, troubleshoot any problems with use and ensure that the participant isn't experiencing any undue problems from using the headset. Beyond this, if the participant continues to struggle with using the apparatus independently (i.e. through muscle weakness) then a member of the research team will be available daily to assist. Participants in the inpatient setting will be assessed for any current episodes of delirium prior to using the headset using the CAM-ICU. If a participant progresses to independent use of the VR headset, formal delirium assessments will not be performed as it would be expected that any bout of delirium would preclude independent usage, but research staff will continue to check in with participants regularly.

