15.3 Data storage and access

All study records will be identified via a unique study identifier. Any hard copy documentation containing study data will be stored in locked cabinets in the Clinical Research Centre, Cwm Taf Morgannwg University Health Board. Only the consent forms will contain identifiable personal data. Only employees of Cwm Taf Morgannwg University Health Board will have access to these documents.

All electronic study records will be held on secure servers and be protected using personal network passwords. Pseudonymised study records will be made accessible to collaborating investigators from institutions outside the sponsor organisation through secure file sharing software such as Microsoft Teams.

Personal identifiable data (largely restricted to participant contact details) will be held within the sponsor organisation in a participant management database that will be protected by additional password encryption. Access will be restricted to limited individuals on the delegation log. Where participants may contact the study team to indicate their interest in taking part in the study or for general correspondence with the research team about their participation in the study, they will do so via the [contact] address. The shared mailbox enables monitoring of study correspondence, management of the study and other key activities to be performed by several different team members. This reduces the onus on a single team member to attend to all issues and means that there is no single point of failure in study management. Participants contacting the shared mailbox will involve sharing their contact details (name and e-mail address) outside of the sponsor organisation and will be done voluntarily by the participants.

16 Protocol/GCP non-compliance

The Principal Investigator should report any non-compliance to the study protocol or the conditions and principles of Good Clinical Practice to the CTR in writing as soon as they become aware of it.

17 End of Study definition

The end of the study is defined as the date of final data capture to meet the study endpoints. In this case end of study is defined as the completion of the final qualitative interview in Phase 3 of the study.

Sponsor must notify the main REC of the end of a clinical study within 90 days of its completion or within 15 days if the study is terminated early.

18 Archiving

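### Non-serious adverse events must be recorded, but the plan cites the wrong section for the procedure and states no enquiry about motion sickness or headache once assisted headset use ends, least of all at home

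*Protocol*

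**What the plan says.** **Recording rule.** After the SAE procedure, Protocol Section 12.5.1 disposes of every other event in one sentence: "All other AEs should be reported on the relevant CRF in the study database following the CRF procedure described in Section 16". Section 16 opens: "The Principal Investigator should report any non-compliance to the study protocol". It contains no CRF procedure.

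**Named harms.** Section 12.4 lists two expected events of headset use, motion sickness and headache, and describes both as usually mild.

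**Exposure and supervision.** Section 11.3 states: "Up to 25 participants will be recruited to receive the intervention for 2 weeks in the in-patient setting". Of patients discharged before the two weeks are complete, it says "they will be able to take the headset home with them". On supervision it states: "For at least the first two days of the intervention, the participant will be assisted by a member of the research team". One purpose of that help is to make sure that nobody is "experiencing any undue problems from using the headset". For a participant who still cannot manage alone afterwards, "a member of the research team will be available daily to assist". Participants who become independent are no longer formally assessed for delirium, but staff are to keep checking in on a regular basis. The frequency and content of those check-ins are not given.

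**Reporting windows.** Section 12.5.1 has SAEs reported from consent to completion of follow-up. Section 12.5.2 has the study team continue SAE reporting until the participant receives the last part of the intervention. No window is given for non-serious events.

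**The concern.** Because both named harms are usually mild, they will rarely meet an SAE definition. They therefore fall almost entirely under the single sentence on other adverse events, and that sentence points to the wrong place. Nothing else in the protocol says when, how or by whom a participant is asked about them.

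Three things are at stake:

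- **Uneven observation.** A patient too weak to use the headset alone may be seen every day. An independent or discharged patient may not be asked at all. A low count in independent or home use could then mean that nobody asked.
- **Relevance to later work.** A secondary objective in Section 5.2 is a framework for adapting the kit to other healthcare and at-home settings. Home use is where the least observation is stated.
- **Reading adherence.** Completion of intervention sessions is a progression criterion in Section 5.3. The headset records duration and content only. Without a symptom question, low use because of nausea is hard to tell from low use because of lack of interest, except through what emerges at interview.

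Section 21.1 plans no monitoring at site, so the gap is unlikely to be noticed while the study runs.

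**Working it through.** No sample size, power or error rate bears on this point. The check sets the sections side by side and adds one ratio.

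**1. Does the cross-reference lead anywhere?**
- Section 12.5.1 cites Section 16, which is Protocol/GCP non-compliance.
- Two other references are also one section too high. Section 12 cites 13.2, while the study-specific SAE requirements are in 12.2. Section 6.1 cites 22.1, while monitoring is in 21.1. So 16 was probably meant as 15.
- Reading it as Section 15 does not complete the instruction. Section 15.2 describes outcome assessments that participants complete on paper or electronically, and no adverse event form.

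**2. Is ascertainment scheduled elsewhere?**
- Table 2 has rows for consent, demographics, eligibility, outcome measures, intervention, adherence and interviews. It has none for adverse events.
- The measures in Section 11.3.1 are EQ-5D, ICECAP-A, the Brief Resilience Scale, the Richards Campbell Sleep Questionnaire and DASS-10. As described there, none asks about motion sickness or headache. The EQ-5D pain and discomfort domain is generic.
- The interview topics in Section 11.3.1 are feasibility and acceptability of the intervention and of the outcome measures.

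**3. How much of the intervention has a check aimed at headset problems?**
- Intervention length: 2 weeks = 14 days (Section 11.3).
- Guaranteed assisted period: at least 2 days (Section 11.3).
- Guaranteed share: 2/14 = 14.3%.
- Remainder for someone independent after day 2: (14 − 2)/14 = 12/14 = 85.7%.
- Upper end, for an inpatient who needs help every day: 14/14 = 100%.

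**4. What is stated after the assisted period, by setting?**

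| Setting | Stated contact | Harms enquiry stated? |
|---|---|---|
| Inpatient, still struggling | Team member available daily | Not beyond the aim of the assisted period |
| Inpatient, independent | Regular check-ins, frequency not given | No; content unstated |
| Discharged with headset | Follow-up assessments by post, email or telephone | No |

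**5. Can the amount of under-recording be computed?** No. The protocol gives no event rate, onset pattern, check-in frequency, or share of participants who become independent or go home.

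**The case against.** The strongest case on the other side has five parts.

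- **Supervision does not stop at day two.** The two days are a minimum, daily help remains available to those who need it, and staff keep checking in on independent users. This stands. A reader might infer that harms are checked only on the first two days, and the text does not support that. But the check-ins appear in a passage about delirium and carry no stated question about symptoms, and none of this reaches a patient at home.
- **Data are also gathered during delivery.** Section 15.1 describes interview data at two points, one during intervention delivery, and participants can always report spontaneously. This stands in part. Section 11.3.1 and Table 2 place participant interviews after the intervention and give the delivery period to staff interviews, so the sections do not fully agree, and the stated topics are not harms.
- **The cross-reference is clerical.** This stands, given the other off-by-one references. The duty to record on a CRF survives the slip, and the layout of an adverse event form is commonly left to the CRF itself. When and whether to ask is a different matter and belongs in the protocol.
- **The source-data table in Section 15 proves little.** It has no adverse event line, but it also omits demographics, adherence and SAEs, so it is plainly not exhaustive. This stands, and the point does not rest on that table.
- **Safety is not an objective.** Sections 5.1 to 5.4 list no safety outcome, the study is classed as low risk, and the kit is adapted from a CE-marked device. This stands and limits the weight of the point. It does not remove the protocol's own requirement that all other adverse events be recorded.

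**Conclusion.** The point holds as a gap in ascertainment that is cheap to close. Followed exactly, the plan requires non-serious adverse events to be recorded, cites a section with no procedure for doing so, and states no enquiry about the two harms it names once assisted use ends. The guaranteed floor of targeted checking is 2 of 14 days (14%). Actual coverage may be anything up to 14 of 14, depending on how much help a patient needs. The gap is clearest for patients who finish the two weeks at home.

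A reader might go further and conclude that the adverse event record will be incomplete and biased towards supervised users, or put a figure on the loss by assuming an event risk and an onset pattern. The documents support neither step. They show that intensity of observation depends on independence and discharge, which makes differential capture a plausible risk. They give no input from which its occurrence or size could be derived.

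The conclusion rests on the measures being as described in Section 11.3.1 and on the check-ins having no set content beyond what Section 11.3 states.

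**What to change.** 1. In Section 12.5.1, change the reference from Section 16 to Section 15.2, and say in 15.2 how adverse events are recorded.
2. Add an adverse event row to Table 2, and state the window over which non-serious events are collected.
3. Ask one fixed question, covering motion sickness, headache and any other problem with the headset, at contacts that already exist: assisted sessions, inpatient check-ins, and the week-2 and any later follow-up by telephone, paper or electronic link. Ask it of patients and of relatives who use the headset.
4. Record the setting of use with each event (assisted inpatient, independent inpatient, home) and tabulate the events descriptively. With up to 25 patients the cells will be small, so no comparison between settings should be attempted. A table of this kind fits the tabular summary already planned in Section 14.2.
5. Reconcile the SAE reporting windows in Sections 12.5.1 and 12.5.2.

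The cost is some protocol wording, one CRF page and a short question at contacts already planned. The downside is a small added burden on participants and staff, and a higher recorded count of adverse events, which should be explained as the result of asking.
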